Effectiveness will be assessed via our primary, secondary and patient-centered outcomes.

Adoption is a measure of potential intervention uptake by WIC. We will quantitatively assess number of provider referrals for study entry.

Implementation will be examined on both the participant level and the WIC provider level. At the participant level, we will measure intervention engagement via: 1) number of responses to self-monitoring text prompts, text response time, and the type/frequency of texted videos viewed; 2) type/frequency of FB or Instagram posts and/or likes; and 3) number/duration of WIC provider visits and calls completed. Relying on an approach by Olson and colleagues, we will examine the extent to which level of engagement is associated with gestational weight gain.⁸⁵ We will also evaluate the consistency of the intervention across different patient/provider subgroups. At the WIC provider level, we will examine process data stored in our web application and perform chart reviews to assess documentation of weight-related counseling to measure intervention delivery fidelity.

Maintenance of weight change will be assessed at 6- and 12-months postpartum. We will determine the proportion of women in each treatment group at (+/- 0.9kg) or below early pregnancy weight by 6 months and 12 months postpartum. While observational data repeatedly suggest that excessive gestational weight gain is the strongest predictor of postpartum adiposity,³ few studies have evaluated this relationship in the context of a clinical trial. With participant consent, we will additionally abstract their infant's weight and length from their pediatrician visits. These will be used to approximate measures at 6-months and 12-months of age and assess maintenance of intervention effects on infant weight/length.

iii. **Data analysis plan:**

1. **Primary aim.** We will use Fisher's exact test (for raw intervention effects) as well as multivariable logistic regression (for adjusted intervention effects), testing the effect of treatment group on the odds of excessive gestational weight gain while simultaneously adjusting for covariates discovered to be unbalanced between the trial arms at baseline. We will consider interaction effects of treatment by relevant baseline predictors when needed, (e.g., age, parity, BMI, and gestational age at enrollment), to evaluate the assumption of equal intervention effects between the 2 arms with respect to these covariates. Data will be analyzed using an intention-to-treat (ITT) approach where subjects are analyzed according to their treatment assignment at randomization, regardless of level of engagement. Since an ITT analysis is planned, 2 methods are proposed for accounting for missing data. First, multiple imputation methods will be used to estimate weight at 36-38 weeks' gestation based on intermediate outcomes, mediating variables, and data collected on subjects with complete follow-up.^{87,88} A second approach will utilize model-based analyses with direct maximum likelihood methods.⁸⁹

Additionally, to take advantage of the longitudinal nature of this study, we will treat weight as a continuous measure, employing an advanced mixed-effects modeling approach to estimate individual and mean weight trajectories over time by treatment group. We will supplement weights collected by research staff with available electronic health record prenatal weight data abstracted from WIC and/or participants' obstetric records; we and others have found that the absolute agreement between research and prenatal clinic measured weights is extremely high, providing strong support for exchangeability.^{90,91} Benefits of this modeling approach include: 1) ability to accommodate all available measured prenatal weight data; 2) allowance for varying and/or unequally-spaced intervals between measurements; and 3) high variability in the number of longitudinal assessments expected across subjects. Longitudinal trajectories could be modeled using splines or kernel density.⁹² They will allow for an unbiased estimation of the overall intervention effect on gestational weight gain to better understand non-linear, dynamic changes in weight over time.

2. **Additional aims.** We will use parallel strategies to those described above for secondary and patient-centered outcomes.

If continuous data are not normally distributed, log or square-root transformation will be considered. We will control for confounders and evaluate effect modification as needed. RE-AIM outcomes will be analyzed in an exploratory fashion.

Additional analyses investigating the mediating influence of dietary and physical activity changes will use bootstrapping for standard errors to estimate the direct, indirect, and total effects.⁹³⁻⁹⁵

3. **Cost-effectiveness.** We will conduct the cost-effectiveness analysis from both the societal perspective (payer and participant) and a third party payer's perspective using an Activity Based Costing approach. We will identify the key activities that drive overall costs, and assign all labor, materials and supplies, and contracted services costs to these activities using intervention tracking forms that have been successfully applied in prior studies.⁹⁶⁻⁹⁸ All costs will be valued at market rates. We will also identify which costs are sunk (e.g., software development) costs and which are incremental costs; only the latter will be used in analysis. Participant time spent on intervention activities (excluding time costs for physical activity and other behavioral modification) will be tracked via surveys at assessment visits, and these costs will be monetized based on the average hourly wage of participants (or an imputed wage for those not working). These surveys will also include questions from the Medical Expenditure Panel Survey to identify differences in healthcare utilization across arms.⁹⁹

Once all costs are properly accounted for, we can derive an average incremental cost of healthy lifestyle intervention relative to WIC usual care. Although data does not exist on long term outcomes of mothers and children as a function of gestational weight gain to support a comprehensive cost effectiveness analysis in terms of costs per quality adjusted life years saved, we will report the incremental cost per unit reduction in prevalence of excessive gestational weight gain. We will compare this estimate to interventions targeting similar outcomes.¹⁰⁰⁻¹⁰² We will present results for the base case and for reasonable ranges of key parameter values. These estimates will prove useful to decision makers who may be interested to fund the intervention.

4. **Power and sample size.** Sample size estimates were determined to ensure power for detecting differences in trial arms on the primary study outcome, the proportion of women with excessive gestational weight gain. We used results from

our own preliminary studies along with published data from earlier trials in obese pregnant women to approximate our ability to detect differences in weight gain between trial arms. In our pilot study, Healthy Babies, 37% of intervention participants gained in excess of IOM guidelines compared to 66% of usual care.¹⁹ We recognize, however, that our pilot study's sample size was small, and thus, ***we have made a more conservative assumption for the power analysis in this proposal*** – 15% difference between healthy lifestyle intervention and usual WIC care arms (e.g., prevalence of 40% in the intervention arm vs. 55% in usual care) – based on data that includes a range of between-group differences, from 12% to 30%.^{15,49} Sample sizes of 186 per arm will provide power of at least 0.8 with a 2-sided alpha of 0.05. If the difference is 20% (e.g., 40% vs. 60%), the power will be at least 0.96. Conservatively assuming we will lose 15% for miscarriage or loss to follow-up, the required sample size is 219 subjects per arm or 438 total.

10) Withdrawal of Subjects

Participation in this study is completely voluntary. Participants may refuse to participate or stop participation in this study at any time and it will not affect their present or future care at WIC or Temple University.

11) Privacy & Confidentiality

Information about study subjects will be kept confidential and managed according to the requirements of the Health Insurance Portability and Accountability Act of 1996 (HIPAA). Those regulations require a signed subject authorization informing the subject of the following:

- What protected health information (PHI) will be collected from subjects in this study
- Who will have access to that information and why
- Who will use or disclose that information
- The rights of a research subject to revoke their authorization for use of their PHI.

In the event that a subject revokes authorization to collect or use PHI, the investigator, by regulation, retains the ability to use all information collected prior to the revocation of subject authorization. For subjects that have revoked authorization to collect or use PHI, attempts should be made to obtain permission to collect at least vital status (i.e. that the subject is alive) at the end of their scheduled study period.

Subjects will be identified only by a coded identification number. No names will be used on any source documents. Data entered into the database for analysis in RedCap (which is stored on Temple University's HIPAA secure servers) will contain only the subject identification numbers. Source documents will be stored in a locked file at CORE during active data collection and analysis. Only IRB and

Good Clinical Practice (GCP) trained staff will have access to individually identifiable information under supervision of the PI. The privacy, security, and durability of accumulated personal health information are of paramount importance. Specifically: physical access to computing resources (hard drives, servers, networking equipment) is secure, audited, and restricted to skilled, IRB- and GCP-trained personnel; virtual access (login and system administration) is encrypted, audited, and limited to skilled personnel; all software and servers are reachable only via a virtual private network (VPN); and all communication between our software's application programming interface (API) and third-party software is encrypted using SSL.

All surveys and measures will be administered in a private room – either at CORE, WIC, from a staff member's home, or in the patient's home – to allow patients to feel that their answers are private or confidential.

Study staff will communicate with participants via text message. In the Healthy Lifestyle Group, staff will also communicate with participants by phone. Intervention participants will be asked to weigh themselves on a cellular-connected scale. To send and receive phone calls and text messages, and to store study information and weights, we use companies such as Twilio, Google Cloud Platform, and BodyTrace. These companies will take measures to keep information safe on their servers (such as keeping the data encrypted), but no system is completely safe. This information is also included in the participant consent.

12) Risks to Subjects

a. Potential Risks:

Few risks or discomforts are anticipated or likely in this study. Participants may become uncomfortable when talking about their height or weight. It is assessed that these risks are small. All data will be collected over the phone with staff in a private room during the call.

Participants may be uncomfortable answering questions (e.g., about demographics, dietary intake, or health-related quality of life). To minimize any discomfort by participants, staff members will be hired who have experience interacting with pregnant women. Additional instruction regarding appropriate interactions will be provided by the PI. When possible, questionnaires will be administered on mobile phones, tablet, or computer, with the use of audio to minimize social desirability bias and literacy demands. Further, participants who indicate being uncomfortable or appear to be uncomfortable will be given the opportunity to withdraw their participation at any time throughout the study. Discomfort will also be minimized by informing participants that all data will only be labeled with an identification (ID) number and only appropriate research staff will have access to this number.

The healthy lifestyle intervention itself presents few risks to participants. The intervention will encourage weight gain as recommended by ACOG and the Institute of Medicine during pregnancy based on BMI.^{76, 85} Their recommendations have been evaluated and are part of the standard of care for pregnant women. Women will be encouraged to participate in physical activity and eating behaviors that are associated with the best outcomes for mother and fetus. Recommendations for physical activity and nutrition will not differ from established public health recommendations. There is a small risk of muscle sprains, other soft tissue injuries, or bone injuries from exercise; however, participants will be given information about proper stretching techniques and the importance of a warm-up and cool-down period to minimize injury.

Additionally, there is a small risk of loss of privacy due to the Facebook group and/or Instagram profile. All study participants have 3 different options for the manner in which they join the Facebook group, each corresponding to the level of privacy they wish to have: Option 1) Participants can choose to link their own existing private Facebook account with the private Facebook group, allowing other study participants to see all of the content on their individual Facebook page; Option 2) Participants can choose to link their own existing private Facebook account with restrictions to the private Facebook group, allowing other participants to see only the content on their individual Facebook pages that they permit them to view; Option 3) Participants can choose to create an alias Facebook account exclusively for joining the intervention, prohibiting the other participants from accessing any of the content on the individual Facebook pages that they maintain for personal, private use. It is important to recognize that non-members will not be able to view the group or obtain group membership. The primary purpose of the Facebook group is to enhance weight-related support and mentoring through online postings (videos, links and contests), “likes”, and Facebook mail. Participants will be told that they should use their discretion with the amount and extent to which they share sensitive information to the other members of the group. For Instagram, there are two options: Option 1) Participants can use their own existing Instagram profile to follow the private study Instagram profile; Option 2) Participants can choose to create an alias Instagram account exclusively for following the study Instagram profile, prohibiting other participants from accessing any of the content on their individual Instagram profile that they maintain for personal, private use. Study staff will review and respond to any comments made or messages sent on both social media platforms to dispel misinformation, provide support, and monitor progress, distress and/or side effects from the program.

b. Protection Against Risk:

- i. **Planned procedures for minimizing or protecting against potential risks.** Information about study subjects will be kept confidential and managed according to the requirements of the Health Insurance Portability and Accountability Act of 1996 (HIPAA). Subjects will be identified only by a coded ID number. No names will be used on any source documents. Data entered into the database for analysis will contain only the subject ID numbers. Source documents will be stored in a locked file cabinet in a secure location on Temple's Health Sciences Campus. Only the PI and Project Director will have access to participant contact information (e.g., name, phone number, postal address and/or email address). The web application used by WIC staff and Facebook platform will be maintained by a qualified vendor (Louis Clotman Design, LLC) and ***be fully compliant with HIPAA guidelines for patient privacy and data security.*** The vendor will comply with current data security standards as they evolve (also see Privacy addressed in section 11 above).
- ii. **Additional protections for pregnant women and their fetuses.** There is minimal risk to both mother and fetus – the intervention will encourage weight gain as recommended by ACOG and the Institute of Medicine during pregnancy based on BMI. Their recommendations have been evaluated and are part of the standard of care for pregnant women. Women will be encouraged to participate in physical activity and eating behaviors that are associated with the best outcomes for mother and fetus. Recommendations for physical activity and nutrition will not differ from established public health recommendations.
- iii. **Additional plans for ensuring medical or professional intervention in the event of adverse effects to the subjects.** It is not anticipated that there will be any adverse events. However, in the unlikely event that an adverse event does occur, the PI ([name] MD) will be notified immediately and any intervention will be handled directly by the PI (in consultation with [name] MD, Co-Investigator and Obstetrician/ Gynecologist, and [name] MD, Professor of Population Medicine and Nutrition at Harvard Medical School). [name] is the designated medical monitor for the study; [name] is the lead Safety Officer. Both physician-scientists have a high degree of understanding about the potential risks involved with modifying antenatal diet and physical activity. All adverse events will be reported within a timely manner to the Temple University IRB. All IRB guidelines on reporting and monitoring adverse events and data will be followed strictly. Participants will be immediately referred to their obstetric providers if any clinical problems (including physical and emotional issues that do not qualify as an adverse event) are detected. Drs. [name] and [name] will also be available to assist participants and staff with clinical questions/concerns over the entire study period.

iv. **Provisions to Monitor the Data to Ensure the Safety of Subjects.**

Annually, we will generate a summary report for [name] (safety officer) review, including: description of recruitment and retention status; tables showing enrollment and demographics; and tables showing adverse events. In the present study, we expect that most, if any, reported complications will result from activities unrelated to the intervention.

13) Potential Benefits to Subjects

a. ***Potential Benefits to Research Participants and Others:***

Potential benefits for intervention study participants include improved lifestyle and a reduction in maternal/fetal adiposity and cardiometabolic risk. An additional benefit for some participants may be personal satisfaction in being part of a study that may have major public health implications for the community. Of particular importance is the fact that this project aims to provide an intervention in a culturally appropriate and sustainable manner. However, no benefit from participation can be guaranteed.

b. ***Risks to the Subjects are Reasonable in Relation to the Anticipated Benefits:***

Risks to subjects are minimal and therefore reasonable in relation to the anticipated benefits to the research subjects and society as a whole.

14) Costs to Subjects

If participants agree to take part in this research, they will receive \$100 after completing all CS/EN questionnaires and being officially enrolled (to reimburse participants for time and travel). All enrolled participants will also receive a diaper bag and a scale to weigh themselves at each study time point after their CS/EN call. Mothers in the intervention group will have a water bottle, measuring bowls & spoons, and a cookbook included in their bag. Enrolled participants will additionally receive \$75 after completion of their 36-week gestation call, and \$50 after completion of their 6-month and 12-month postpartum calls. Total compensation for completing all assessments will be \$275.00 (for both groups). Participants will either be texted or emailed VISA e-gift cards (preferred method) or mailed plastic VISA gift cards at the end of each visit. Participants in the intervention group will also be eligible to win a monthly raffle prize, valued between \$75.00 and \$100.00. Intervention participants will receive 1 raffle entry for each monitoring text they send. Monthly raffles will be held (run by study staff) on the last day of every month and winners will be contacted via text message. Septa passes will also be provided for transportation (if needed).

15) Informed Consent

All subjects for this study will be sent a consent form via e-mail or mail prior to the combined CS/EN call or visit. During the initial call/visit, study staff will review the Informed Consent describing this study and providing sufficient

information for subjects to make an informed decision about their participation in this study. The consent form is submitted with this protocol for review and approval by the IRB. The formal consent of a subject, using the IRB-approved consent form must be obtained before that subject is submitted to any study procedure.

Consent will be obtained electronically via Redcap prior to any study procedures being completed. Study staff will be trained to consent patients and provide a detailed explanation of all procedures, risks, and benefits.

Additionally, participants will be sent or given paper copies of their signed Informed Consent Form, the HIPAA Authorization, and the Medical Record Release forms (prenatal, delivery, infant, and WIC)

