Study Title: Partnering with WIC to Prevent Excessive Weight Gain in Pregnancy

NCT Number: NCT03707834

Documents Included: IRB Approved Protocol with Statistical Analysis Plan

Date of IRB Approval: 09/21/2021

1) Abstract of the study

Institute of Medicine guidelines for weight gain in pregnancy are clear, but evidence-based treatment approaches are not widely available. This evidence gap is particularly pressing for medically vulnerable women - those who are low income and often racial/ethnic minorities. These women have the highest rates of obesity, but almost no resources to support weight control in pregnancy. Without intervention, most will exceed Institute of Medicine recommended gains and incur significant morbidity for themselves and their children. There is preliminary data from our group supporting the efficacy of digital health platforms for delivering antenatal obesity treatment among the medically vulnerable. However, our inexpensive, easily scalable approach has not been integrated and tested in real world settings, limiting broad reach and dissemination potential. Dissemination considerations are especially pressing for socioeconomically disadvantaged and minority populations because of these groups' higher obesity risk, greater potential for experiencing obesity-related comorbidities in pregnancy, and limited finances to afford alternative treatments. The Women, Infants and Children (WIC) Food and Nutrition Program is the leading public health nutrition program for pregnant women and their children in the US, and thus, it is in a unique position to meaningfully impact the obesity epidemic among the more than 9 million disadvantaged participants it serves annually. Yet no demonstrations of effective gestational weight gain interventions exist in WIC. We propose a pragmatic trial designed to rigorously test our antenatal obesity treatment approach integrated into Philadelphia WIC community clinics. We have long-standing relationships with WIC staff and prior experience conducting pragmatic clinical trials in under-resourced settings. We will randomize 438 African American and Latina Philadelphia County WIC participants with obesity in early pregnancy to one of two treatment arms: 1) usual WIC care; or 2) healthy lifestyle intervention arm, which includes empirically supported behavior change goals, regular self-monitoring text messages with automated feedback, tailored skills training materials, and counseling from WIC nutritionists. Our primary outcome is prevalence of excessive gestational weight gain; we will additionally examine changes in diet and physical activity, health-related quality of life, and rates of adverse pregnancy outcomes. We will use the RE-AIM (Reach, Effectiveness, Adoption, Implementation, Maintenance) framework to evaluate the intervention's dissemination potential and cost effectiveness in the WIC setting. The proposed project will constitute the first systematic translation of a comprehensive antenatal obesity treatment program focused on low-income, racial/ethnic minorities, using the strengths of mHealth and WIC provider counseling for intervention delivery.

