
2) Protocol Title

Partnering with WIC to prevent excessive weight gain in pregnancy

3) Investigator

[name], MPH

4) Objectives

a. Primary specific aim: To determine whether the healthy lifestyle program lowers the prevalence of excessive gestational weight gain, compared to usual WIC care. Primary hypothesis: Participants randomized to the healthy lifestyle intervention arm will demonstrate significantly lower prevalence of excessive gestational weight gain, compared to those randomized to usual WIC care.

b. Additional aims:

- i. To compare trial arms with respect to changes in diet and physical activity, and rates of adverse pregnancy outcomes (including glucose intolerance, hypertension, and infant macrosomia).
- ii. To utilize the RE-AIM framework to evaluate the intervention's dissemination potential in WIC. We will assess: reach into the patient population; effectiveness on outcomes; organizational adoption; consistency of implementation; and maintenance of effects on 6- and 12-month maternal/child postpartum weights.
- iii. To quantify the intervention's cost-effectiveness.

5) Rationale and Significance

Nearly two-thirds of pregnant women exceed Institute of Medicine (IOM) weight gain guidelines.¹ Excessive gestational weight gain not only adversely affects the current pregnancy – by increasing risk of diabetes and hypertension, cesarean delivery, and infant macrosomia – but it also promotes new or persistent obesity in women and their children.^{2,3} Ethnic minority women are at particular risk of greater gains because they are more likely to enter pregnancy obese,⁴ reside in obesogenic environments,⁵ and adopt obesity promoting behaviors (e.g., high caloric intake, physical inactivity).⁶⁻⁸ However, these high risk women also suffer from a paucity of treatments. Without intervention, the implications are clear: most will exceed recommended gains in pregnancy and incur significant morbidity for themselves and their children.^{9,10}

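### Diet is to be compared between arms as change, and nothing commits the analysis to adjusting for the baseline value; it should be in the model always, not only when the arms look unbalanced

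*Combined protocol and SAP*

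**What the plan says.** All references are to the combined protocol and SAP.

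- **Aim.** Section 4.b.i: "To compare trial arms with respect to changes in diet and physical activity, and rates of adverse pregnancy outcomes". The abstract (Section 1) has a similar list that also names quality of life: "we will additionally examine changes in diet and physical activity, health-related quality of life, and rates of adverse pregnancy outcomes".
- **Measurement.** Diet comes from one ASA24 recall at the enrolment contact and one at the end of pregnancy (Section 9.d.ii.1, Table 1). The SF-12 is part of the questionnaires given at baseline and at each follow-up (Section 9.b.i).
- **Analysis of secondary outcomes.** Section 9.d.iii.2: "We will use parallel strategies to those described above for secondary and patient-centered outcomes". The strategies referred to, in Section 9.d.iii.1, are Fisher's exact test, a regression "adjusting for covariates discovered to be unbalanced between the trial arms at baseline", and a mixed-effects model for weight trajectories.
- **Further adjustment.** Section 9.d.iii.2: "We will control for confounders and evaluate effect modification as needed".
- **Transformation.** Section 9.d.iii.2: "If continuous data are not normally distributed, log or square-root transformation will be considered". It does not say whether this means raw values or changes.
- **Postpartum weight.** Section 9.d.ii.5 (Maintenance) names one summary of maternal weight: "the proportion of women in each treatment group at (+/- 0.9kg) or below early pregnancy weight". RE-AIM outcomes are described as exploratory.

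**The concern.** An outcome measured before randomisation is usually one of the best predictors of the same outcome at follow-up. Here it is collected in both arms and would cost nothing to use. The only explicit covariate rule makes its use depend on the observed baseline data, so in most trials run under this plan it would be left out.

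Subtracting baseline does not replace adjusting for it. A change score gives the baseline a fixed coefficient of 1, whereas the best coefficient is close to the baseline to follow-up correlation. With one recall per visit, that correlation may be well below 1, and the change then carries the day-to-day noise of two recalls. The plan states no power for diet, so there is no stated margin to absorb avoidable noise. What is at stake is a real dietary effect being estimated less precisely than the collected data allow.

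**Working it through.** **The plan's own figure.** No sample size is given for diet, so the primary calculation only fixes the evaluable number. For 40% vs 55%, 80% power and two-sided 0.05, the continuity-corrected formula gives 186 per arm (173 without correction). Fisher's exact power at 186 per arm is 0.81. Allowing for 15% loss, 186/0.85 = 218.8, so 219 per arm. The plan's figures reproduce, and 2 × 186 = 372 women are taken as evaluable below.

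**Inputs.** Equal variance σ² at baseline and follow-up; correlation r, which the documents do not give, varied from 0.2 to 0.7; 1:1 allocation (Section 8.c.vii); an imbalance trigger of p<0.05, also assumed, because the plan does not define unbalanced.

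**Case A: change score, baseline never added.**
- Variance per woman of the change: 2σ²(1−r).
- Variance per woman after baseline adjustment (ANCOVA): σ²(1−r²).
- Ratio: 2(1−r)/(1−r²) = 2/(1+r).
- Information lost: 1 − (1+r)/2 = (1−r)/2.

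**Case B: change score, baseline added only if unbalanced.** Let D be the between-arm difference in baseline means. The change-score estimate equals the ANCOVA estimate minus (1−b)D, where b, the fitted slope, is about r. Under the rule this extra term remains only when |z| < 1.96, z being D over its standard error. For standard normal z:

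E[z²; |z|<1.96] = 0.95 − 2 × 1.96 × 0.0584 = 0.721.

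The variance ratio to ANCOVA is therefore 1 + 0.721(1−r)/(1+r), and the information lost is 1 − 1/ratio. At r = 0.3: 1 + 0.721 × 0.7/1.3 = 1.388, and 1 − 1/1.388 = 28%.

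| r | Loss, never added (A) | Loss, added if p<0.05 (B) | Equivalent number of 372, A | Equivalent number of 372, B |
|---|---|---|---|---|
| 0.2 | 40% | 32% | 223 | 251 |
| 0.3 | 35% | 28% | 242 | 268 |
| 0.4 | 30% | 24% | 260 | 284 |
| 0.5 | 25% | 19% | 279 | 300 |
| 0.6 | 20% | 15% | 298 | 315 |
| 0.7 | 15% | 11% | 316 | 330 |

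Simulation of Case B at 186 per arm agrees to within about a percentage point: 32%, 27–28% and 23–24% at r = 0.2, 0.3 and 0.4; 19–20% at 0.5; 11–12% at 0.7.

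**In terms of power, Case A only.** For an assumed effect of 0.3 SD at 186 per arm, change score against ANCOVA: 0.63 vs 0.84 (r = 0.2), 0.69 vs 0.86 (0.3), 0.83 vs 0.92 (0.5), 0.96 vs 0.98 (0.7). Case B lies between each pair. Below r = 0.5, the variance 2(1−r) exceeds 1, so the change score is less precise than ignoring baseline altogether.

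**Transformation.** Log and square root are undefined for negative numbers, and changes in intake can be negative. Applied to raw intakes, square root always works and log fails only at zero. Zero is a real possibility: one intervention goal is to have no sugary drinks at all (Section 9.c.iii.1), so a zero on a single recalled day is a target state.

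**The case against.** **An aim is not a model.** Section 4.b.i states a question; no sentence says that a raw change will be the dependent variable. Arms can be compared on change with baseline in the model, and the treatment estimate is then identical to ANCOVA. This stands, and it makes the loss conditional. What the plan does not do is commit to that model.

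**The reference back to the primary aim could bring in the mixed model.** It could, but how baseline would enter is not stated. With two time points and complete data, an unconstrained arm-by-time model gives the same contrast as the change score. The gain appears only if baseline is a covariate or the baseline means are constrained to be equal.

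**The imbalance rule catches the worst cases.** It does, and so Case B is smaller than Case A. Differences below the trigger still pass into the estimate, and those account for most of the lost precision.

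**Stronger readings that the documents do not support.**
- A reader might infer a flat loss of about a third. In Case A that needs r near 1/3, and the documents give no r. One figure need not suit both diet and SF-12.
- A reader might take quality of life to be analysed as a change. It is absent from Section 4.b.i, and in the abstract the word for change need not govern it.
- A reader might conclude that the transformation step is impossible. The text speaks of continuous data and of considering a transformation; read as raw intakes, it mostly works. The gap is an unstated scale.
- A reader might fault the postpartum cut-off as ignoring baseline. It is defined relative to early-pregnancy weight, and the outcome is exploratory.

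**Conclusion.** The point holds as a better method available at almost no cost. The only explicit rule carried to secondary outcomes is imbalance-driven, supplemented by confounder control where judged necessary, and the outcome's own baseline value is never guaranteed a place in the model.

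If diet is analysed as change under that rule, the loss relative to always adjusting is about 32% to 11–12% for r from 0.2 to 0.7; if baseline is never added, it is 40% to 15%. These figures assume equal variances, a p<0.05 trigger and a change score as the dependent variable. The lower correlations, and so the larger losses, are plausible for single 24-hour recalls, but that is a judgement and not a figure from the plan.

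The harm is mainly to precision. Under randomisation the average estimate is not biased, although in any one trial a baseline difference below the trigger shifts it. Only secondary outcomes are affected.

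**What to change.** Add to Section 9.d.iii.2:

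1. For every continuous secondary outcome with a baseline measurement (ASA24 intakes, and SF-12 however it is framed), the follow-up value is regressed on arm with the baseline value always in the model, whether or not the arms differ at baseline. The stratification factors, weight status and ethnicity, can be included in the same model.
2. Any log or square-root transformation is applied to the raw baseline and follow-up values, not to their difference. Where zero intake is possible, a method that allows zeros is named in advance. Only log-scale results are back-transformed to ratios; square-root results do not convert that way.
3. Optionally, keep the ±0.9 kg proportion and add 6- and 12-month maternal weight, adjusted for baseline weight, as an exploratory continuous analysis. A yes/no cut of a normally distributed measure keeps φ(z)²/[p(1−p)] of the information: 0.49 if 20% meet it, 0.64 if 50% do.

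The cost is SAP wording; no new data are needed. The small downsides are extra exploratory comparisons from item 3 and the need to choose a method for zeros in item 2.
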